## 1.0 Background

Short Interpregnancy Intervals have Adverse Consequences for Adolescents. Healthy People 2020 identifies short interpregnancy intervals (IPIs), i.e., pregnancies within 18 months of a previous birth, as an issue of national importance [1]. Short IPIs pose risks for mothers and newborns alike [2] including preterm birth, low birth weight, small for gestational age, and placental abruption [3-5]. IPIs less than 12 months increase risk of neonatal death [6]. One in three American women ages 15-44 have short IPIs [7]. Short IPIs disproportionately affect low income, undereducated, women of color [8] accounting for an estimated 8% of low birth weight and preterm infants among African American and Hispanic mothers [9]. However, adolescents (ages 15-25) bear the greatest burden [3, 10]. With one in five births to adolescents a repeat birth [7], over two thirds following short IPIs [11-13] leaving young mothers to care for multiple babies. Postpartum contraception significantly, and perhaps uniquely, lengthens IPIs [14-16]. Injectables reduce short IPIs, with only 14.2% of postpartum adolescent depot medroxyprogesterone acetate (DMPA) users with short IPIs [17]. Women using long acting reversible contraception (LARC), implants and intrauterine devices (IUDs), have optimal IPIs compared to users of oral contraceptive pills and condoms [18]. Initiation of contraception prior to hospital discharge is a crucial strategy, as 10-40% of women do not attend a postpartum visit [19]; 50% of women resume sexual activity before the standard postpartum visit [20, 21] and ovulation can return by postpartum day 25 [22].

A.2. Research and New Policies Support Immediate Postpartum Contraception. All contraceptive methods, save combined hormonal contraception, are safe for use within 48 hours of delivery. Immediate postpartum implant use independently predicts longer IPIs in adolescents [25] as well as general study populations [18]. Significant research demonstrates adolescent interest in immediate postpartum LARC [26], as well as its cost effectiveness in both adolescent and general populations of women [27-29]. Immediate postpartum IUD placement, despite expulsion risk, was found effective in randomized control trials of immediate versus delayed placement, with equal rates of use at six months post vaginal and post cesarean delivery [30, 31]. However, our team has identified several barriers to receiving IUDs for adolescents after hospital discharge, including outdated IUD eligibility requirements and lack of insurance coverage [23]. Hitherto, Medicaid reimbursement policy bundles payment within a global delivery fee, significantly hindering immediate LARC placement [32, 33]. Now, seventeen states, including Illinois, and the District of Columbia allow providers to bill for immediate LARC placement.

A.3. A History of Coercive Contraceptive Practices Calls for Patient-Centered Postpartum Contraceptive Care. Yet, caution is needed given a long history of contraceptive coercion of low-income communities. In 2001, the Institute of Medicine (IOM) published Crossing the Quality Chasm, highlighting patient-centered care as a model for improving quality of care [34]. Within this model, care is respectful and responsive to individual patient preferences, needs, and values. Patients are actively engaged in making decisions about their health care and continuously informed and educated on all the care options [35, 36]. Significant research shows the benefits of “patient activation” and “engagement”. Actively engaged patients have lower healthcare utilization [37], greater satisfaction [38, 39], and better health outcomes [40-42]. Patient-centered approaches have been advocated for within contraception counseling and delivery [43, 44] and positively influences adolescent contraceptive use [45].

A.4. Current Provider Practices May Limit Patient-Centered Postpartum Care. Provider practices can limit patient-centered care through contraceptive underuse and overuse. Only 50% of obstetrician gynecologists offer implants at all due to lack of patient interest and provider training [46]. Despite research to the contrary [47], progestin-only methods such as DMPA have been denied due to concerns about lactogenesis or hormones in breast milk [30]. Surveys of obstetrician gynecologists and family physicians show lack of knowledge of LARC placement [48]. Despite endorsement by major professional organizations such as the American College of Obstetricians and Gynecologists (ACOG) and the CDC, many clinicians deny adolescents LARC [49]. Yet, as barriers to contraception decrease there is also a risk of contraceptive overuse. Many providers have adopted directive or first-line counseling approaches in which LARC is recommended above all others [50][51].

A.5. Tailored Patient Approaches are Needed to “Activate” Patients. Racial and ethnic minorities in general are less willing to participate in health care decision-making [52]. Latinos and African Americans report worse patient-provider relationships and communication [53]. These patients also receive less information regarding treatment and are less likely to be asked about their preferences [54]. Populations with low activation are likely to benefit from improved activation [55]. There is a need for interventions designed for the characteristics of the population (e.g., demographic, culture, literacy, age) [56].

A.6. Technological Interventions Can Support Health Care. Interactive, computer-based programs provide a novel platform for delivering health interventions [57]. Tailored, theory-based interventions have been effective for assisting with smoking cessation [58], community counseling interventions for repeat births among low-income African American adolescent mothers [59], promoting adherence to antiretroviral medications [60], and increasing awareness of diabetes complications [61]. Touchscreen computer and tablet interventions have increased likelihood of choosing highly effective contraception [62, 63]. Young women are willing to receive sexual health information via digital media, perceiving these delivery routes as private and accessible [64, 65].

## **2.0 Rationale and Specific Aims**

The proposed study seeks to evaluate a post-partum app. Using a pre-post survey design the following hypotheses will be tested:

H1: Do end users (pregnant women age 15-25) find the app usable, feasible, and acceptable and recommend continued development?

H2: After using the app, users will have increased information about IPIs.

H3: After using the app, users will have increased intention to communicate about IPIs with their provider.

H4: After using the app, users will have increased Patient Activation Measures.

## **3.0 Inclusion/Exclusion Criteria**

Inclusion criteria are:

- (1) Being 18-25 years old
- (2) Currently pregnant.
- (3) Identify as African American/Black

Exclusion criteria are:

Being male  
Being over age 25.  
Not identifying as African American/Black

The rationale for exclusion criteria is to focus on adolescent and young adult pregnancy and pregnancy prevention among this group.

#### **4.0 Recruitment and Enrollment**

We will recruit up to 40 young pregnant women who are between 15-25 to evaluate our app. Participants will be paid \$35 upon completion of study activities. Participants will be recruited from ACCESS prenatal care or maternity community clinic waiting rooms.

Prenatal case management teams will inform patients there is a research study they may be eligible for. If potential participants are interested they will be told to contact a research team member in the waiting room. Research team members will administer a short screener survey on an iPad to ensure eligibility. The survey will inform potential participants if they are eligible or not. If participants are eligible they will be taken through informed consent/assent.

Additionally flyers will be posted directing interested potential participants to contact an ACCESS staff member or text a number (that will be a study phone, that is a Ci3 phone used only for study purposes) to enroll in the study. ACCESS team members will refer potential participants to the research team member in the waiting room. The same screener and informed consent/assent procedure will be performed.

#### **5.0 Study Procedures**

Participants will be given a consent/assent form to read. A researcher will ask the participant if they have any questions. Once all questions have been resolved, or if there are no questions, the participant will sign the consent/assent form. Consent/assent forms will be stored in a locked filing cabinet in a locked University of Chicago office.

All participants will be given an iPad tablet containing a brief pre survey to fill out. This survey will include questions on demographics, contraception knowledge, contraception use, and patient activation measures (readiness of patients to take charge of their own healthcare). This survey will take 20-30 minutes to complete.

Next participants will use the app on the iPad for 5-10 minutes. Participants will be instructed to go through all parts of the app.

Lastly, participants will complete a brief post survey on the iPad. The survey will include questions on usability, feasibility, and acceptability of the app, patient activation measures, and contraception knowledge. This survey will take 20-30 minutes to complete.

All study activities will take between 40-70 minutes to complete. All study activities will take place in the waiting room.

At the conclusion of the post surveys, participants will be paid and participation in the study will end.

Participants will be paid \$35 in visa gift card or cash equivalent after completion of the post survey.

## **6.0 Reporting of Adverse Events or Unanticipated Problems involving Risk to Participants or Others**

Participants are exposed to few risks in this study. The informed consent/assent will assure participants complete confidentiality throughout the study. Possible adverse events that are unanticipated will be brought to the attention of the Principal Investigators and Co-investigator, and reported immediately to the IRB. The IRB will determine whether it is appropriate to stop the study protocol temporarily or will provide suggestions/modifications to the study procedures. Possible modifications include adding these possible adverse events to the consent/assent form and re-consenting all study participants. The PI will be responsible for monitoring participant safety on a monthly basis at regularly scheduled research meetings. They will keep a written log of all adverse events and ensure that the IRB is contacted immediately. They will also keep a log of the outcome of IRB decisions regarding adverse events and apprise the research team of any changes that need to be made as a result of IRB decisions. If a participant discloses suicidal ideation, any type of violence, or homicidal intent, the Research Team will assess the level of risk and determine the best course of action (e.g., sending the participant to the emergency room, notifying the police).

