## **7.0 Privacy/Confidentiality Issues**

Study records that identify the participant will be kept confidential. All participants will be assigned a unique study identifier. Informed consents/assents with the subjects' names will be stored at the UC and only accessible to designated research staff. Printed consent/assent forms will be stored in a locked filing cabinet in a locked University of Chicago office and they will only be available to the research team described in the proposal. All reports, manuscripts, and presentations will omit identifying information. Participants are informed of these protections in the consent/assent form.

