## **8.0 Record Retention**

All data will be stored on a secure, password-protected computer or iPad tablet and printed consent/assent forms will be stored in a locked filing cabinet in a locked University of Chicago office. They will only be available to the research team.

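### Section 6 has the consent/assent promise unlimited confidentiality, yet the same paragraph allows police notification after certain disclosures, so the promise cannot be kept as written

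*Combined protocol and SAP*

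**What the plan says.** Section 6.0 describes what the consent document will promise: "The informed consent/assent will assure participants complete confidentiality throughout the study". No qualification is attached, either to the kind of information covered or to the circumstances.

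The last sentence of the same section sets out a response to three kinds of disclosure: "If a participant discloses suicidal ideation, any type of violence, or homicidal intent, the Research Team will assess the level of risk". The team then decides how to respond. Referral to emergency care and contact with the police are mentioned. Both actions are given as examples, and the choice is left to the team.

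Two later sections also deal with confidentiality:

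- Section 7.0 says "Study records that identify the participant will be kept confidential". It adds study identifiers, restricted access to signed forms and the removal of identifying details from reports, and then says "Participants are informed of these protections in the consent/assent form". It names no circumstance in which information could leave the team.
- Section 8.0, on stored data and printed forms, says "They will only be available to the research team", also without exception.

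The consent steps in Sections 4.0 and 5.0 mention no limit to confidentiality.

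**The concern.** An assurance described as complete and lasting throughout the study leaves no room for the team to report what a participant said to the police. The protocol nevertheless reserves that possibility a few sentences later. Followed literally, the plan has participants promised something that the team has kept discretion not to honour.

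What is at stake is participant protection. A person deciding what to tell a researcher should know beforehand when it may be passed on. Consent comes before the pre survey, so that is when the limits need to be stated. The point may matter more if minors take part. Section 3.0 sets the age range at 18 to 25, but the aims and Section 4.0 refer to ages 15 to 25, and assent is mentioned throughout. On the wording of Section 4.0, participants under 18 could receive this assurance.

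**Working it through.** No formula applies. The point depends on no rate, effect size or sample size calculation, and the plan gives no figure to reproduce. The check sets the relevant statements side by side.

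| Place | What it covers | Limit stated? |
|---|---|---|
| Section 6.0, assurance | Confidentiality in general, for the whole study | None |
| Section 6.0, last sentence | Team response to three types of disclosure; two example actions | Permits action involving parties outside the team |
| Section 7.0 | Identifying records, access to signed forms, publications | None |
| Section 8.0 | Stored data and printed forms | None |
| Sections 4.0 and 5.0 | Recruitment and consent steps | None |

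**Step 1: can both sentences in Section 6 hold together?** Of the two example actions, sending someone to an emergency room need not involve the team passing on what was said. Notifying the police clearly does. If that option is used, the unqualified assurance is broken. If it is never used, the assurance happens to be kept, but it was still given while the option to depart from it was reserved. As worded, the sentences are incompatible.

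**Step 2: does another section supply the missing limit?** Section 7.0 is narrower, because it speaks of records rather than everything a participant says. But it says participants are told of the protections and lists no exception to them. Section 8.0 restricts access to stored material and lists none either. These two sections do not create a second contradiction, since a report of a spoken remark need not release a stored record. They matter only because neither cures the conflict in Section 6.0.

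**Step 3: how many people are affected, and how often?** Section 4.0 allows up to 40 participants, all of whom would receive the assurance. The survey topics listed in Section 5.0 are demographics, contraception knowledge and use, patient activation, and the usability, feasibility and acceptability of the app. None concerns violence, self-harm or homicidal intent. Exposure would therefore come mainly from spontaneous disclosure during a single session, which the plan puts at 40 to 70 minutes. The documents give no expected frequency; it is probably low.

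**The case against.** The strongest objection is that participants receive their assurance from the consent/assent form, and that form was not available for this review. If it states the usual limits, nobody is misled and the fault is one loose sentence in the protocol. This stands as a limit on the finding: the form cannot be called defective. It does not rescue the protocol sentence, which says what the form will assure. Either the form follows the protocol and promises too much, or it states limits and the protocol misdescribes it. The sentence needs correction in both cases.

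A second objection is that the closing sentence of Section 6.0 can be read as a specific exception to the general assurance, and that ethics reviewers and staff would see both together. That is a fair reading for staff, who are told what to do if such a disclosure occurs. It does not help participants, because the assurance is described as what they are told and the exception is not.

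A third objection is that the event is rare, police contact is discretionary, and Sections 7.0 and 8.0 concern stored records. All of this is correct, and it keeps the point from ranking higher. It does not remove it: the assurance is given to everyone at consent, before anyone knows whether the discretion will be used, and the plan itself foresaw such disclosures.

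**Conclusion.** The concern holds. Section 6.0 contradicts itself: it has the consent/assent assure confidentiality without limit, and it lets the team pass certain disclosures outside the study. Sections 4.0, 5.0, 7.0 and 8.0 state no limit that resolves this.

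Up to 40 participants would receive an assurance the team may not keep. The number for whom it would actually be broken cannot be estimated from the documents and is probably small. There is no effect on sample size, endpoints or analysis.

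The conclusion rests on the protocol's description of the consent/assent form, not on the form, and on the plain reading that notifying the police conveys information about a participant outside the team. It takes no view on which response to a disclosure is right. This is a correction that should be made, and confidence in it is high because both conflicting sentences stand in the same paragraph.

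**What to change.** Reconcile the two sentences in Section 6.0. In place of the unlimited assurance, state that confidentiality is maintained as described in Section 7, except where the research team acts on a disclosure as set out at the end of Section 6. Repeat that limit in Section 7.0, where the protections conveyed to participants are listed. Section 8.0 concerns stored material and can stand, unless a report would draw on stored records; in that case a cross-reference to Section 7.0 is enough.

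Then check that the consent/assent form tells participants these limits before the pre survey. The risk-assessment procedure is unchanged.

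The cost is an edit to two sections and a check of one form. If the form turns out to carry the unlimited promise, it must be revised as well, which would probably need ethics review and, for anyone already enrolled, a decision on whether to re-consent. A possible downside is slightly fewer spontaneous disclosures; the documents give no basis for estimating how many.

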## **7.0 Privacy/Confidentiality Issues**

Study records that identify the participant will be kept confidential. All participants will be assigned a unique study identifier. Informed consents/assents with the subjects' names will be stored at the UC and only accessible to designated research staff. Printed consent/assent forms will be stored in a locked filing cabinet in a locked University of Chicago office and they will only be available to the research team described in the proposal. All reports, manuscripts, and presentations will omit identifying information. Participants are informed of these protections in the consent/assent form.

## **8.0 Record Retention**

All data will be stored on a secure, password-protected computer or iPad tablet and printed consent/assent forms will be stored in a locked filing cabinet in a locked University of Chicago office. They will only be available to the research team.

## **9.0 Statistical Analysis Plan**

Descriptive statistics will be used to describe the study sample and the feasibility, usability, and acceptability of the app. Appropriate parametric and nonparametric paired statistics will be used for outcomes assessed at pre- and post-test based on data normality and how well assumptions are met.

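### Does Section 2 promise a test of H1 that Section 9 does not deliver, and is part of H1 left without a measure?

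*Combined protocol and SAP*

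**What the plan says.** Section 2.0 (Rationale and Specific Aims) opens its list with "Using a pre-post survey design the following hypotheses will be tested". The first entry is "H1: Do end users (pregnant women age 15-25) find the app usable, feasible, and acceptable and recommend continued development". H2 to H4 follow, and each predicts an increase after app use: in information about interpregnancy intervals, in intention to talk to the provider about them, and in patient activation.

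Section 5.0 (Study Procedures) sets the order as pre survey, 5 to 10 minutes with the app, then post survey. Of the pre survey it says: "This survey will include questions on demographics, contraception knowledge, contraception use, and patient activation measures". Of the post survey it says: "The survey will include questions on usability, feasibility, and acceptability of the app, patient activation measures, and contraception knowledge".

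Section 9.0 (Statistical Analysis Plan) is two sentences long. The first is "Descriptive statistics will be used to describe the study sample and the feasibility, usability, and acceptability of the app". The second begins "Appropriate parametric and nonparametric paired statistics will be used for outcomes assessed at pre- and post-test" and leaves the choice of method to normality and how well assumptions are met.

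**The concern.** Two things look wrong when these sections are read together.

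First, H1 stands under a sentence that announces hypothesis tests in a pre-post design. Participants have not seen the app at the pre survey, so no part of H1 can have a pre value, and the paired methods in Section 9.0 cannot reach it. Section 9.0 gives it description only. A reader of Section 2.0 might expect a test result for H1 and find none. Because H1 has no stated criterion for a positive answer, almost any summary could also be presented as support.

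Second, H1 has four parts, and the fourth, whether users would advise that development go on, is named nowhere outside H1. It is arguably the part closest to the decision that an app evaluation should inform. If the questionnaire had no such item, the answer could not be recovered later, because participation ends when the post survey is complete and no follow-up contact is described.

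**Working it through.** The plan gives no threshold, alpha, power or sample-size derivation for H1, so there is no figure to reproduce. The check sets the three sections side by side.

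**Inputs**

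- H1 parts (Section 2.0): usability, feasibility, acceptability, advice to continue development. Total 4.
- Pre-survey topics (Section 5.0): demographics, contraception knowledge, contraception use, patient activation. Total 4.
- Post-survey topics (Section 5.0): usability, feasibility, acceptability, patient activation, contraception knowledge. Total 5.
- App topics in the descriptive sentence (Section 9.0): feasibility, usability, acceptability. Total 3.

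**Where each part of H1 is named**

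| H1 part | Pre survey | Post survey | Section 9.0 |
|---|---|---|---|
| Usability | no | yes | described |
| Feasibility | no | yes | described |
| Acceptability | no | yes | described |
| Advice to continue development | no | not named | not named |
| Count | 0 of 4 | 3 of 4 | 3 of 4 |

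Topics in both surveys: contraception knowledge and patient activation, which makes 2, of which 0 belong to H1. H1 parts named in neither Section 5.0 nor Section 9.0: 4 − 3 = 1. The observations behind the concern are therefore accurate.

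**Step 1: does the missing test matter?** The lead-in to Section 2.0 can be read as describing the whole study, which has a pre survey and a post survey. An outcome taken from the post survey alone still arises within that design. Nothing in Section 2.0 says that every entry gets a paired or inferential test. H1 is phrased as a question, while H2 to H4 each state a direction of change. Section 9.0 makes the same division: description for the app ratings, paired methods for outcomes measured twice. Section 5.0 fits this too, since the ratings come after use, the only time they can be given. Read together, the sections tell the analyst to describe H1 from the post survey. Renaming H1 a descriptive aim would leave the data collected, the summaries produced and the paired comparisons as they are.

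**Step 2: does the unnamed fourth part matter?** Section 5.0 says what each survey will include and does not claim a full list. Neither Section 5.0 nor Section 9.0 names an item, scale or score for any outcome. The same comparison applied to H3 gives a similar result: intention to communicate with the provider is in neither survey list. Leaving out one part of H1 is thus in line with the level of detail of the whole plan and is no evidence that the item is absent. A question on whether work on the app should go on could also sit naturally within an acceptability block. Whichever applies, an analyst with the responses would tabulate them with the other app ratings.

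**The case for a change.** The strongest case for acting is that the remedy is nearly free and can only be applied in time before data collection: a sentence in Section 2.0, a clause each in Sections 5.0 and 9.0, and at most one survey item. H1 lists advice to continue separately from acceptability, so a reader may fairly expect the plan to say if one measure serves both. If no item exists, the loss is permanent. A yes-or-no question with no stated criterion for yes also leaves room for a generous reading of the results.

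Part of this stands. The fourth part is named only in H1, and calling H1 a hypothesis to be tested is loose wording. But low cost is not a reason for change unless something is gained. The case that an item is missing depends on a questionnaire that the documents do not contain, and if the item is there the correction is wording only. A criterion for a positive answer, or a prescribed reporting format with counts and denominators, is a reporting preference in a small descriptive evaluation: Section 9.0 already tells the reader that the app ratings are described, and a descriptive summary makes no claim to have passed a test.

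One limit applies in the other direction. It would be too much to say that H2 to H4 are untouched by this kind of gap. H3 is framed as a change, and its outcome is also not named in either survey list. That is a separate matter from whether H1 is described or tested, and the conclusion on H1 does not settle it.

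**Conclusion.** No change to the plan is needed on this point. The mismatch between Sections 2.0 and 9.0 is a clerical matter of calling a descriptive question a hypothesis. Post-use ratings summarised descriptively are the right treatment in a study of up to 40 participants, and relabelling would change no result. The one part of H1's four that is not named in Sections 5.0 and 9.0 is a gap in detail, of the kind this topic-level plan has throughout and that analysts fill sensibly by reporting the item with the other ratings.

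The conclusion rests on two assumptions. The first is that the post survey captures users' advice on further development, either as its own item or within acceptability; the documents neither show nor exclude this. The second is that H1 will be reported as description, as Section 9.0 says, and not presented as a confirmed hypothesis. If the first assumption failed, one part of H1 would go unanswered, while the other three parts and the paired analyses would stand as planned. Confidence is moderate, because the questionnaire cannot be seen.
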